The anatomical laboratory provides a controlled environment, ideal for simulating surgical procedures, allowing the analysis of multiple variables that influence the effectiveness of the procedure and cannot be controlled in clinical practice (4–14). Recently, the Principal Investigator (PI) developed, in collaboration with the University of Toronto, a navigation system that allows for the quantification of the workspace to define a specific surgical approach (14–19). This new method has been used in several anatomy laboratories, including those at the Universities of Brescia, Toronto, and Geneva, to conduct comparative quantitative studies on various neurosurgical, otolaryngological, and skull base surgery approaches. Some of the results obtained have been published in international scientific journals (14–24).

Objective

The main objective of this study is to conduct a preclinical and systematic analysis of the various cranial and spinal surgical approaches to evaluate their potential and limitations in an objective manner. Attention will be particularly focused on the study of skull base approaches, spinal approaches, quantitative studies, exploration of anatomical variations, and the validation of new surgical approaches and related instruments.

Endpoints

Primary Endpoints:

1. Quantification of Work Volume and Exposed Area in Crano-Spinal Surgical Approaches

Work volume represents the three-dimensional operative space created by each crano-spinal surgical approach. Quantification will be performed using BrainChop imaging software on standardized CT scans. Segmentation will follow predefined protocols to ensure reproducibility. Higher values indicate a larger and more accessible operative corridor. Exposed area corresponds to the two-dimensional anatomical surface revealed by each surgical approach. Measurements will be obtained from CT-based reconstructions using the same standardized segmentation workflow. Higher surface values reflect wider surgical exposure.

Unit of Measure: cubic millimeters (mm³) and square millimeter.

Time Frame: Measurements will be obtained twice with BrainChop software for each approach on every specimen: before the dissection using baseline CT imaging and after completing the approach using repeat CT imaging on the same day.

Secondary Endpoints:

1. Analysis of anatomical variations influencing surgical approaches.
2. Validation of new surgical instruments and techniques on cadaveric specimens.

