The specimens will be cataloged according to their source, and anonymized data provided by the donor centers will be entered into a database. Proper storage of the specimens will take place at the Institute of Pathological Anatomy (Head: [name]) at the Catholic University of the Sacred Heart. Non-fixed specimens will be stored frozen at -20°C in dedicated freezers, while fixed specimens (with formalin) will be stored at 4°C in a solution (formaldehyde, glycerol, alcohol reagent, and water).

Variables

The approaches will be performed in a modular manner, from the least invasive to the most extensive. Various surgical approaches will be simulated using surgical instruments dedicated to skull base surgery, spinal surgery, and in both macrosurgical and microsurgical visualization modes.

The quantification of the working volume and the exposed area for each surgical approach will be calculated with an open-source software (BrainChop) on the CT scans of the specimens obtained before and after surgical dissection. For each specimen's CT scan, the area of interest exposed by the different approaches to be compared will be outlined using the BrainChop software (14-24).

Error and Control

To minimize potential sources of error, rigorous control methodologies will be implemented during data collection. Each analysis will be repeated multiple times to ensure the accuracy of the results.

Sample Definition

Given the descriptive nature of the study, a formal sample size determination is not required. However, we estimate that 35 cadavers will be enrolled over the three-year period.

Statistical Analysis

Quantitative variables will be summarized as means and standard deviations, while qualitative variables will be reported as absolute and relative frequencies (percentages). The effectiveness of the training will be evaluated by testing the mean difference of scores obtained in tests administered before and after the training, using the paired Student's t-test or the Wilcoxon test.

The difference in execution times between different techniques will be tested using ANOVA or the Kruskal-Wallis test. Linear models with random intercepts will be used to compare surgical volumes and exposed areas. A 95% confidence interval will be estimated using the bootstrap resampling method.

Results with $p < 0.05$ will be considered statistically significant. Statistical analysis will be performed using STATA software (StataCorp® LLC, College Station, TX, USA).

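### Repeating the outlining cannot remove a systematic difference between approaches that are recognisable on the CT; the protocol states no masking and names no common target for the primary measurements

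*Protocol*

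**What the plan says.** The primary endpoints are working volume and exposed area, both measured with BrainChop on CT.

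- **What is measured.** Primary Endpoints: "Exposed area corresponds to the two-dimensional anatomical surface revealed by each surgical approach". Variables adds that, for each specimen's scan, "the area of interest exposed by the different approaches to be compared will be outlined using the BrainChop software". That sentence ends with a reference to sources 14 to 24.
- **On which images.** Variables: "on the CT scans of the specimens obtained before and after surgical dissection". The time frame under Primary Endpoints asks for two measurements per specimen and approach, with this timing: "before the dissection using baseline CT imaging and after completing the approach using repeat CT imaging on the same day". Procedure, in contrast, has the CT repeated after dissection in only some of the cases.
- **Stated safeguards.** Primary Endpoints: "Segmentation will follow predefined protocols to ensure reproducibility", and for exposed area "Measurements will be obtained from CT-based reconstructions using the same standardized segmentation workflow". Error and Control: "rigorous control methodologies will be implemented during data collection", without description, and then "Each analysis will be repeated multiple times to ensure the accuracy of the results".
- **What is not stated.** The protocol names no anatomical target or landmark set common to the approaches compared. It mentions neither masking of the person who outlines nor an independent reader.
- **How the values are used.** Statistical Analysis compares volumes and areas between approaches by linear models with random intercepts, with significance at p < 0.05.

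**The concern.** Both primary values depend on where a border is drawn. The region is described by what the approaches expose, and a CT taken after dissection shows the opening, so whoever outlines can tell which approach was used. The expected direction is also known: Variables orders the approaches from least invasive to most extensive, and Primary Endpoints treats larger values as better access.

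Against this the protocol sets repetition and says that it secures accuracy. Repetition cannot do that. If one approach is consistently outlined a little more widely, the excess recurs at each repeat and survives averaging. The random intercept does not help either: it absorbs differences between specimens, not a shift tied to the approach.

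At stake is the main comparison. An outlining difference enters volume and area directly and cannot afterwards be told apart from a true difference in exposure. The third year is meant to validate new approaches, and a new-versus-standard comparison is where such a difference would mislead most.

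**Working it through.** The protocol gives no figure on this point, and its 35 specimens are an estimate without a formula, so there is nothing to reproduce. Two illustrations show the mechanism and the range of possible size.

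**Inputs from the protocol:** 35 cadavers in total (Sample Definition); significance level 0.05 (Statistical Analysis).

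**Assumptions:** two-sided test; one paired comparison of two approaches with no true difference; 35 or 12 specimens in that comparison, since no number per comparison is given; the SDs and the bias as shown below.

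**1. What repetition does.** Express the systematic shift b in SDs of the true paired difference. Let random outlining error have SD 0.5 per repeat, averaged over k repeats. Then

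ncp = b × √35 / √(1 + 0.25/k), and P(reject) = Φ(ncp − 1.96) + Φ(−ncp − 1.96).

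For b = 0.2 and k = 1: ncp = 0.2 × 5.916 / 1.118 = 1.058, so P = 18.5%. For k = 10: ncp = 0.2 × 5.916 / 1.012 = 1.169, so P = 21.5%.

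| Shift b | 1 repeat | 10 repeats |
|---|---|---|
| 0 | 5.0% | 5.0% |
| 0.1 | 8.3% | 9.0% |
| 0.2 | 18.5% | 21.5% |
| 0.3 | 35.5% | 41.8% |
| 0.5 | 75.4% | 83.2% |

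Without a systematic shift, repetition leaves the error rate at its nominal level. With one, repetition makes a false difference slightly more likely to be declared.

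**2. How the size depends on the bias.** If one approach is outlined wider by a fraction x in linear extent, area grows by (1 + x)² − 1 and volume by (1 + x)³ − 1. For x = 5%: 1.05² = 1.1025 (+10%) and 1.05³ = 1.158 (+16%).

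For exposed area, with the SD of the within-specimen difference at 20% of the mean, ncp = [(1 + x)² − 1] × √n / 0.20, referred to a noncentral t with n − 1 degrees of freedom. For x = 2% and n = 35: 0.0404 × 5.916 / 0.20 = 1.195, which gives 0.21.

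| Linear bias x | Area shift | P(significant), n = 35 | P(significant), n = 12 |
|---|---|---|---|
| 1% | 2.01% | 0.09 | 0.06 |
| 2% | 4.04% | 0.21 | 0.10 |
| 3% | 6.09% | 0.42 | 0.16 |
| 5% | 10.25% | 0.84 | 0.37 |

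The SD matters as well. For a shift of exactly 10% and n = 35, the probability is 0.97, 0.82 or 0.48 at an SD of 15%, 20% or 30%; for n = 12 it is 0.56, 0.35 or 0.18.

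**The case against.** A reader might infer that no target is fixed before outlining. The protocol does not support this. It asserts predefined segmentation rules and one standardised workflow, and the outlining sentence in Variables cites eleven sources (14 to 24). The content of the rules is not shown and may sit in another document; whether they fix a target is unknown. That sentence can even be read as describing one region per specimen, common to the approaches compared, although the definition of exposed area under Primary Endpoints points to a separate surface for each approach. The text is ambiguous here rather than plainly wrong.

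A reader might also infer that the primary comparison is biased. Nothing in the protocol says that outlines are drawn freehand, that one person does every repeat, or that anyone favours an approach. The figures rest on assumed biases, and at 1% with 12 specimens the error rate is close to nominal. Using all 35 cadavers in one comparison is also generous, because they are spread over cranial and spinal approaches.

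What remains is narrower. The stated purpose of the segmentation rules is reproducibility, which is not the same as freedom from a shift tied to the approach. The wider promise of control methods is not described. The one control that is described is credited with something it cannot deliver. Nor is this a matter to leave to an analysis plan, since no later analysis removes a bias already in the outlines.

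**Conclusion.** The point holds in a limited form. The protocol asserts segmentation rules aimed at reproducibility, names no common target, states no masking, and credits repetition with accuracy. Because the post-dissection CT reveals the approach, a systematic outlining difference can remain in the primary comparison, and repeats would not reveal or remove it.

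The size cannot be derived from the document. Under the stated assumptions (SD 20% of the mean, two-sided 0.05), the chance of declaring a purely artificial area difference runs from about 0.06 (1% bias, 12 specimens) to about 0.84 (5% bias, 35 specimens). These figures show that the comparison can reflect outlining, not that it will. The change should be made, and early: Setting gives 15/10/2025 as the start of specimen recruitment, and outlines already drawn with the approach known cannot be made masked afterwards.

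**What to change.** **Variables.** State that the target region is outlined once per specimen on the baseline CT before dissection, locked, and carried by bone registration to every post-approach CT. Keep exposed area in mm² as the primary measure and report it in addition as a percentage of the locked target.

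**Error and Control.** Do the planned repeats of both area and volume on files with specimen and approach labels removed, in shuffled order and without sight of earlier results. Use their mean, report repeatability, and replace the word *accuracy* by *repeatability*.

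**Procedure and Primary Endpoints.** Reconcile the statement that CT is repeated after dissection in only some cases with the time frame that requires it for each approach on every specimen. The measurement needs the post-approach CT.

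**Cost.** Protocol wording, file handling and one registration step per scan. The baseline CT and the repeats are already planned, and no extra reader is needed. If post-dissection scanning is at present intended for only some cases, the missing scans are a further cost, but one that the primary endpoint's own time frame already implies. Two limits remain: masking is partial because the opening stays visible, and the locked target does not bound working volume, which gains only from the unlabelled, shuffled repeats.

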3. Average operative time for each surgical approach: Determining the average time required to complete each type of surgery (macrosurgical, microsurgical) based on the adopted surgical approach. The analysis will focus on the duration of the intervention for each approach, comparing the relative efficiency of the techniques.
4. Assessment of the perceived difficulty by surgeons during the execution of surgical approaches: Collecting subjective evaluations on the difficulty of the procedure using a difficulty rating scale (e.g., Likert scale), considering factors such as familiarity with the technique, the anatomical complexity of the cadaver, and the ergonomics of the instruments used.
5. Assessment of the visibility of target anatomical structures through different visualization methods: Measuring the visibility of areas of anatomical interest using different visualization methods (macrosurgical, microsurgical). This endpoint will focus on the effectiveness of the different modes in providing clear visibility of critical anatomical structures during the surgical procedure.
6. Acceptability and feedback from surgeons on the use of new surgical techniques and instruments: Gathering feedback from participating surgeons on the new instruments and surgical techniques, evaluating their experience in terms of comfort, ergonomics, ease of use, and ease of learning the techniques employed during the simulation.
7. Effectiveness of dissection and surgical training courses: Measuring the effectiveness of dissection and hands-on training courses using cadaveric specimens, through pre- and post-training tests. This endpoint will focus on the improvement of participants' technical skills, with particular attention to their ability to apply the new surgical techniques learned during the simulations.

Methodology

Study Design

This study is a monocentric, observational, non-profit study that will be conducted on cadaveric anatomical specimens. No drugs or medical devices will be used on human subjects. The study will have a duration of 36 months and will begin after approval from the ethics committee.

The study will be divided into three distinct phases:

- **First and Second Year:** The main objective will be the quantitative analysis of the different surgical approaches. This will be accomplished using the innovative research method already applied by the Principal Investigator (PI) for the preclinical study of skull base surgical approaches.

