- **Third Year:** The focus will be on macroscopically and microscopically visualized skull base and spinal approaches. Quantitative analyses will be conducted, relevant anatomical variations will be explored, and new surgical approaches and related instruments will be validated.

Setting

The anatomical dissections will be performed at the SURGEM Laboratory (located in the Settorian Room of the Institute of Pathological Anatomy at the Catholic University of the Sacred Heart in Rome). Recruitment of specimens began on 15/10/2025 and will continue throughout the study, which is expected to last for three years. The dissections, data collection, and analysis will be carried out continuously during this period.

Procedure

The anatomical specimens will be sourced from the Catholic University of the Sacred Heart's voluntary donation program and the Science Care Program. Sixty percent of the specimens will undergo specific preparations, including arterial and/or venous injections with silicone, consisting of a base and catalyst (Xiameter®, Midland, MI, USA) and colored with Pintasol® (Mixol® Red E-L3mix, Kirchheim unter Teck, Germany). The specimens will undergo high-resolution CT scans, and the DICOM images will be imported into a dedicated neuronavigation system (GTx-Eyes II Approach Viewer, University Health Network, University of Toronto, Toronto, Ontario, Canada). In some cases, CT scans will be repeated after dissection, and new calculations will be made using the neuronavigation software.

CT scans will be performed at the Institute of Forensic Medicine at the Catholic University of the Sacred Heart. The source of the specimens will be tracked and recorded, including:

- Voluntary donation program at the Catholic University of the Sacred Heart, Rome, Italy, in accordance with Italian law (LAW 10 February 2020, No. 10 and DECREE OF THE PRESIDENT OF THE REPUBLIC 10 February 2023, No. 47);
- Science Care, USA.

The dissections will be performed using neuro-surgical instruments specific for skull base surgery available at the SURGEM laboratory:

- Complete set of Rhoton dissectors (Rhodon Micro Dissector).
- Complete set for skull base surgery (Karl Storz®, Germany).

- Zeiss microscope (UCSC 119473).

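### Operative times are tested with ANOVA or Kruskal-Wallis and no specimen term; if one specimen supplies times for several techniques, as seems likely, the test is conservative and loses power

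*Protocol*

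**What the plan says.** Operative time is item 3 of the Secondary Endpoints: "Determining the average time required to complete each type of surgery (macrosurgical, microsurgical) based on the adopted surgical approach". Statistical Analysis fixes the test: "The difference in execution times between different techniques will be tested using ANOVA or the Kruskal-Wallis test". It mentions no specimen, block or repeated-measures term.

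The same section treats its other two comparisons differently. Training scores before and after the course are compared "using the paired Student's t-test or the Wilcoxon test". For the primary endpoint, "Linear models with random intercepts will be used to compare surgical volumes and exposed areas".

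Three places bear on how many approaches share a specimen:
- The time frame of the primary endpoint: "Measurements will be obtained twice with BrainChop software for each approach on every specimen".
- Variables, on each specimen's scan: "the area of interest exposed by the different approaches to be compared will be outlined using the BrainChop software".
- Variables, on the order of work: "The approaches will be performed in a modular manner, from the least invasive to the most extensive".

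The Procedure section is narrower on imaging: "In some cases, CT scans will be repeated after dissection, and new calculations will be made using the neuronavigation software". Sample Definition expects 35 cadavers and gives no power calculation. Results with p < 0.05 are to be called significant.

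**The concern.** One-way ANOVA and Kruskal-Wallis assume independent observations. "ANOVA" alone could mean a repeated-measures form. Its stated rank alternative, however, is an independent-groups test, and the rank counterpart of a repeated-measures ANOVA would be Friedman.

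If several techniques are carried out on one specimen, their times share that specimen's anatomy and state of preservation, so positive correlation is plausible. Comparing techniques within a specimen removes this shared variation, whereas the named tests leave it in the error term. Specimens are few and are divided among cranial and spinal work, so a given comparison may rest on a small subset. What is at stake is the chance of detecting a real difference in operative time.

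**Working it through.** **Inputs.** From the protocol: 35 specimens and a 0.05 threshold. Assumed, because the protocol gives none of them: the number of techniques k, the within-specimen correlation ρ (0.3, 0.5, 0.7), the spread between the lowest and highest technique mean in units of the total SD (other means equally spaced), normal times and equal correlations. The protocol states no power figure to reproduce.

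**Why the test is conservative.** Let n specimens each supply all k techniques, with total variance σ² = 1. The expected mean squares are:
- technique: (1 − ρ) + n Σ(μⱼ − μ̄)² / (k − 1)
- error in one-way ANOVA: 1
- error with a specimen term: 1 − ρ

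With no true difference, the one-way ratio centres near 1 − ρ (0.7, 0.5, 0.3) instead of 1, so the test rejects too rarely.

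For k = 3, n = 35 and a spread of 0.5 SD, the means are −0.25, 0 and 0.25. Then Σ(μⱼ − μ̄)² = 0.125, and 35 × 0.125 / 2 = 2.19.

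| ρ | Technique mean square | Ratio, one-way ANOVA | Ratio, specimen term |
|---|---|---|---|
| 0.3 | 0.7 + 2.19 = 2.89 | 2.89 | 2.89 / 0.7 = 4.13 |
| 0.5 | 0.5 + 2.19 = 2.69 | 2.69 | 2.69 / 0.5 = 5.38 |
| 0.7 | 0.3 + 2.19 = 2.49 | 2.49 | 2.49 / 0.3 = 8.3 |

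**Simulated rejection rates** (complete crossed layout, 20,000 replicates per cell, accurate to about one point; triplets are ρ = 0.3/0.5/0.7):

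| Layout | One-way ANOVA, % | With specimen term, % |
|---|---|---|
| 3 techniques, 35 specimens, no difference | about 1.5–1.7 / 0.3–0.4 / <0.1 | about 5 |
| Same, spread 0.5 SD | 39/36/30 | 58/74/93 |
| Same, spread 1 SD | at least 98 | at least 98 |
| 3 techniques, 12 specimens, 1 SD | 52/51/50 | 68/83/97 |
| 2 techniques, 12 specimens, 1 SD | 67/69/73 | 76/88/98 |

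Kruskal-Wallis behaves like ANOVA: 37/34/28% in the 0.5 SD row. Friedman gives 44/59/81% there, better than the planned tests but below the model when times are normal.

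**Incomplete layout.** If each of 35 specimens receives two of three techniques and the spread is 0.5 SD, power is 27/26/23% for ANOVA against 36/47/67% for a random-intercept model.

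**Zero correlation.** The specimen term then costs 0 to about 4 points. The largest loss is with two techniques, 12 specimens and 1 SD: 65.5% against 61.3%.

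**Nested modules.** Where each approach extends the one before, cumulative times rise by construction, so testing them for equality is uninformative. Power can still be lost: with 12 specimens, extensions averaging 20% of the base module and a coefficient of variation of 0.5, ANOVA rejects in about 20% of runs against 100% with a specimen term. The times of the separate modules have no forced order.

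**The case against.** The strongest objection is that the layout for times is not stated. The phrase about each approach on every specimen describes CT measurement, and outlining areas describes work on a scan. Repeat CT is planned only in some cases. The one described order of work is modular. No section says which specimens are timed for which technique, or whether macrosurgical and microsurgical modes share a specimen. This stands: the point is conditional, and with one time per specimen the planned test is valid.

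The contrast within Statistical Analysis should not be pressed into a contradiction. Training scores are paired within trainee, and the protocol does not name the unit of the random intercepts; specimen is only the natural reading. Different methods can suit different data structures.

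The harm is also limited. This is one of seven secondary endpoints in a study that calls itself descriptive and claims no power. For large differences on all 35 specimens the loss is negligible.

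It could also be said that an analysis plan may settle the layout. It may, but the protocol has already named the tests, and Kruskal-Wallis points to independent groups.

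A reader might infer that ignoring the specimen produces false positives. That would need several times per specimen under the same technique, which the documents do not describe. In the layout they suggest, the error runs the other way.

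**Conclusion.** The point holds in conditional form. The protocol fixes independent-groups tests for operative times, while its other sections make shared specimens likely though not certain. If specimens are shared and times are positively correlated within them, the test is conservative: no added false positives, no bias in the estimated differences, but less power. The loss is substantial for modest differences or small subsets (19 to 63 points at 0.5 SD on 35 specimens: 58 − 39 and 93 − 30) and negligible at 1 SD on all 35.

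These sizes rest on the assumed correlations, numbers of techniques, spreads and normality; only the 35 and the 0.05 come from the protocol. Only secondary endpoint 3 is affected. The documents support neither a claim of inflated type I error nor a claim that the protocol prescribes a time for every technique on every specimen. The change is worth making because it is cheap and suits either layout.

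**What to change.** In Statistical Analysis, state which specimens are timed for which techniques, and that execution times are compared with the random-intercept linear model already planned for volumes and areas: technique as a fixed effect, specimen as a random intercept, and small-sample degrees of freedom.

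- If ranks are preferred and every specimen supplies every technique, use Friedman for three or more techniques, or the Wilcoxon signed-rank test for two.
- Keep ANOVA or Kruskal-Wallis only where each specimen contributes one time.
- For nested modular approaches, report cumulative times descriptively. Incremental module times may be compared with the same specimen-term model, noting that it does not remove sequence effects.

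The cost is a few sentences and a specimen identifier stored with each time, with no new data or software. If the correlation is in fact zero, up to about 4 points of power are lost.

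### If several surgeons supply operative times, the planned ANOVA or Kruskal-Wallis test has no operator term to separate surgeon speed from technique

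*Protocol*

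**What the plan says.** Secondary Endpoints, item 3, makes average operative time per approach an endpoint and gives its purpose: "The analysis will focus on the duration of the intervention for each approach, comparing the relative efficiency of the techniques". The Statistical Analysis section fixes the test: "The difference in execution times between different techniques will be tested using ANOVA or the Kruskal-Wallis test". It calls results with p < 0.05 statistically significant.

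Two other secondary endpoints bear on who operates. Item 4 is headed "Assessment of the perceived difficulty by surgeons during the execution of surgical approaches", and it is to be rated "considering factors such as familiarity with the technique, the anatomical complexity of the cadaver, and the ergonomics of the instruments used". Item 6 is described as "Gathering feedback from participating surgeons on the new instruments and surgical techniques".

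For the primary measurements the same section plans a clustered model: "Linear models with random intercepts will be used to compare surgical volumes and exposed areas". It does not name the grouping factor and does not extend the model to times. Error and Control promises control methods and repeated analyses in general terms only. Nothing states how many surgeons operate, who performs which approach, or that surgeons are balanced over techniques.

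**The concern.** Operative time depends on who operates as well as on the technique. The protocol acknowledges familiarity as a factor for the difficulty rating, but nothing corresponding enters the analysis of time. A comparison with technique as its only factor leaves surgeon differences in one of two places.

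- **Surgeons spread evenly or at random over techniques.** Their differences sit in the error term, and the test is less sensitive than it could be.
- **Surgeons who mostly perform their own technique.** Part of the difference between surgeons appears as a difference between techniques and would be reported as relative efficiency.

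Neither can be repaired later if the operator was not recorded. The second cannot be repaired at all if each technique belonged to its own surgeon.

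**Working it through.** The protocol has no power or sample size calculation for times, so there is no planned figure to reproduce. Sample Definition says only that "we estimate that 35 cadavers will be enrolled over the three-year period".

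**Inputs from the protocol:** 35 specimens (an estimate), significance at 0.05, ANOVA or Kruskal-Wallis between techniques.

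**Assumptions not in the protocol:** 35 independent times (one per specimen, so no specimen clustering), three techniques, three or six surgeons, and a surgeon share of total time variance ρ of 0.1, 0.3 or 0.5. For power, one technique is slower by 1 total SD. Each setting was simulated 3,000 times. The adjusted analysis is an F test for technique with surgeon as a fixed factor.

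**Model.** Time = technique + surgeon effect (variance ρ) + residual (variance 1 − ρ).

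**1. Hand check of the extreme case.** Let each of three surgeons perform one technique only, with n = 35/3 = 11.67 times each. With no technique effect, the expected mean squares are (1 − ρ) + nρ between techniques and 1 − ρ within. The F statistic is therefore inflated by k = 1 + nρ/(1 − ρ). The 5% critical value of F(2, 32) is 3.295. For 2 numerator degrees of freedom P(F > x) = (1 + x/16)^(−16), so the false-positive rate is that expression at x = 3.295/k.

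| ρ | k | 3.295/k | Rate by formula | Rate simulated |
|---|---|---|---|---|
| 0.1 | 2.30 | 1.435 | 0.253 | 0.256 |
| 0.3 | 6.00 | 0.549 | 0.583 | 0.595 |
| 0.5 | 12.67 | 0.260 | 0.773 | 0.772 |

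Formula and simulation agree.

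**2. False-positive rate of one-way ANOVA, no true difference (nominal 0.05).**

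| Allocation of surgeons | 3 surgeons, ρ = 0.1 / 0.3 / 0.5 | 6 surgeons, ρ = 0.1 / 0.3 / 0.5 |
|---|---|---|
| Balanced over techniques | 0.042 / 0.031 / 0.019 | 0.045 / 0.021 / 0.009 |
| Assigned at random | 0.055 / 0.048 / 0.049 | 0.058 / 0.048 / 0.049 |
| Concentrated | 0.140 / 0.361 / 0.531 | 0.085 / 0.188 / 0.301 |
| One technique per surgeon | 0.256 / 0.595 / 0.772 | 0.132 / 0.308 / 0.488 |

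In the concentrated setting, 70% of cases went to a surgeon assigned to that technique and 30% to any surgeon at random. Such a surgeon therefore did 0.7 + 0.3 × 1/3 = 80% of them. Kruskal-Wallis gave nearly the same rates (for example 0.341 against 0.361 for three surgeons at ρ = 0.3). With the surgeon term the rate was 0.044 to 0.062 in the first three allocations. In the fourth, a fixed surgeon term cannot be separated from technique.

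**3. Power for a 1 SD difference, one-way ANOVA → surgeon-adjusted.**

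| Allocation | ρ | 3 surgeons | 6 surgeons |
|---|---|---|---|
| Balanced | 0.1 | 0.674 → 0.702 | 0.656 → 0.681 |
| Balanced | 0.3 | 0.711 → 0.817 | 0.664 → 0.796 |
| Balanced | 0.5 | 0.726 → 0.924 | 0.670 → 0.915 |
| Random | 0.1 | 0.663 → 0.668 | 0.647 → 0.609 |
| Random | 0.3 | 0.699 → 0.773 | 0.669 → 0.720 |
| Random | 0.5 | 0.743 → 0.905 | 0.706 → 0.862 |

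**4. Price of adjusting when it was not needed.** With no surgeon effect (ρ = 0) and concentrated surgeons, the adjusted test has power 0.345 against 0.639 (three surgeons) or 0.322 against 0.652 (six). With balance the price is negligible: 0.634 against 0.641 and 0.649 against 0.658.

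**The case against.** The strongest objection is that the premise is inferred. No section says who performs the timed dissections. Items 4 and 6 concern difficulty ratings and feedback, and the plural does not show that the times within one comparison come from several people. This stands, so the point must be conditional. If one surgeon does all timed work, it falls away.

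A second objection is that ANOVA can carry an operator factor and that model terms are commonly left to a statistical analysis plan. This stands in part. But the protocol names the method, pairs ANOVA with a one-factor rank test that cannot be adjusted, and keeps random intercepts for other outcomes. The point is about that choice, not about missing detail.

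A third concerns design. Variables describes modular approaches from the least to the most extensive, and the primary endpoint's time frame refers to each approach on every specimen. If one surgeon performs the whole sequence on a specimen, surgeons are spread over those techniques and false differences do not arise this way. The documents do not say who operates, so this is possible but not established. It does show that a specimen term belongs in the model and that 35 independent times is a simplification.

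A reader might infer that any uneven sharing of techniques among surgeons destroys the 5% error rate. The documents do not support this. They describe no allocation at all, and under random assignment, which is seldom exactly even, the simulated rate stays at about 5%. Inflation needs systematic concentration of surgeons on techniques, which is neither stated nor implied.

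**Conclusion.** The point holds in conditional form. The protocol implies more than one operating surgeon, tests times between techniques by a method with no operator term named, and reads the result as relative efficiency.

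If several surgeons contribute times to a comparison, the consequence depends on allocation. Under balance or random spread, validity is not threatened, and the loss is power: at a 30% surgeon share, 5 to 13 points for a 1 SD difference. Under concentration, false-positive rates of roughly 9% to 53% occur over the range examined. Where each surgeon keeps to one technique they reach 13% to 77%, and there allocation is the cause, so no model term can cure it.

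All these sizes rest on assumed surgeon numbers, variance shares and allocations. None can be derived from the documents. Operative time is one of seven secondary endpoints in a study that calls itself descriptive, so this is a worthwhile, cheap improvement and not a threat to the main result.

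**What to change.** 1. State who performs the timed dissections. If it is a single surgeon, say so; the operator term is then not needed.
2. Otherwise, record an operator code for every timed procedure from the start.
3. Replace the time test with a linear mixed model for (log) operative time: technique as the effect of interest, operator as a factor (fixed if few, random otherwise), and a random intercept for specimen. The plan already uses random intercepts for volumes and areas.
4. Where practicable, spread surgeons over the techniques being compared. This is an aim, not a condition.
5. Where a technique was performed by one surgeon only, and that surgeon did no comparator, report its times descriptively without an efficiency claim.

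**Cost.** One analysis sentence, one database field and a few degrees of freedom; no extra specimens. Spreading surgeons may need some scheduling. Power falls if surgeons differ little and share techniques unevenly. The loss is small under random assignment (0.647 to 0.609 with six surgeons at a 10% share) but large under strong concentration with no surgeon effect (0.639 to 0.345 with three surgeons). That is a further reason to spread surgeons where possible.
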